Test Up Now Education Program

NCT04304001

Document Date: 1/26/2022

Study Protocol and Statistical Analysis

Study Protocol

The TUNE-UP study is designed as a two-group pretest/posttest pragmatic randomized controlled trial. The study uses the parallel group, two arm superiority trial design with 1:1 allocation ratio. The pragmatic trial aims to test the effectiveness of the intervention in the setting of community health centers. To conduct the intervention trial, 115 participants were randomized at the time of enrollment following completion of the baseline survey. The two experimental arms are: 1) an intervention group which receives the adapted Screen to Save (S2S) educational materials, a tailored brochure for African Americans on colorectal cancer (CRC) screening with input from focus group research, and CHA in-person and cellphone education and counseling supplemented by text messages; and 2) a control group which receives the brochure only. Participants in both study arms received communication from their CHC to receive their stool-based testing kit. The primary outcome is CRC screening by 12-months post-intervention (i.e., receipt of the stool-based test). The intermediary CRC screening outcome is measured at 3-months. Secondary outcomes included CRC knowledge and CRC screening self-efficacy.

Study participants and setting

African American men and women aged 45 to 64 years were included in the study. Participants were screened for eligibility after contacting the project coordinator according to the following inclusion criteria: (1) 45-64 years of age, (2) self-identify as African American, (3) have a working cellphone, (4) resident of Florida, and (5) not up to date with CRC screening per established screening guidelines (i.e., no stool tests in > 9 months, no colonoscopy within 9 years, and no flexible sigmoidoscopy within 4 years) Exclusion criteria are: previous history of CRC, precancerous colorectal polyps, or co-morbid conditions, such as inflammatory bowel disease or Crohn's disease. The project coordinator reads the consent form and obtains verbal consent from eligible persons interested in participating in the trial. Participants receive the consent form signed by the project coordinator with complete information on the study and university contact information when meeting to complete the baseline survey. Based on recruitment and outreach, research participants are patients of one of two community health centers in the greater Tallahassee, Florida area and primarily reside in two North Florida counties: Leon or Gadsden.

Randomization and blinding

The study used the block randomization method. The trial randomized participants at the individual level, stratified by the two CHC sites, using a 1:1 ratio between intervention and control arms. The randomization algorithm used randomly permuted blocks with random block sizes for the purpose of assigning participants. The random selection of block sizes has the advantage of reducing selection bias. The randomization file was produced in SAS 9.4 by the biostatistician. The Principal Investigator informed the study coordinator of study arm assignment using ID numbers after the participant gave consent to participate in the study and completed the baseline survey. If a participant was assigned to the intervention arm, the study coordinator informed the CHA so the participant could be contacted to complete the intervention arm protocol.

Intervention and control groups

All participants received the tailored educational brochure at the initial visit when they completed the baseline survey with the Project Coordinator. The participants who were randomized to the intervention group viewed the S2S video, and the CHA explained the contents if there were questions. This was followed by two weeks of short CHA follow-up calls, concluding with three weeks of motivational text messages on CRC screening. Participants who were randomized to the control group received the educational brochure only. Both intervention and control groups received the FIT from their CHC either in the mail, in person, or during a scheduled patient visit. The CHCs were blinded to study arm.

Community health advisor and educational materials

One CHA was trained by the research team to deliver the 6-week intervention consisting of an initial face-to-face CRC educational presentation using the S2S video, two weeks of phone-call follow-up, and three weeks

of text message follow-up. The intervention was delivered by the CHA to African Americans in North Florida who are patients of the participating CHCs and were not up to date with CRC screening.

The adapted S2S PowerPoint developed by the research team was professionally produced into an approximately 11-minute video narrated by an African American woman. After the participant viewed the adapted S2S video on the CHA's tablet, the CHA asked if the participant wanted to discuss the video or ask any questions. After allowing 2-3 minutes for discussion, the CHA showed the participant a 5-minute FIT patient education video. This video walked the viewer through the steps of completing their at-home screening test. The video was obtained from the manufacturer of the FIT after the research team was informed by CHCs that it was the primary FIT they use. Once the participant finished viewing the second video, the CHA again engaged the participant to discuss any topics or questions the participant may have had. The CHA used a fidelity checklist to document completion of the week 1 educational presentation and make appropriate notes. In weeks 2 and 3 of the intervention, the CHA called the participant to ascertain receipt of the FIT from their CHC and the participant's completion of their FIT. Fidelity checklist phone scripts allow the CHA to document delivery of the calls and facilitated their use of motivational interviewing to address any barriers to completing the screening. In weeks 4-6 of the intervention, participants received one motivational text message per week to encourage them to complete their screening. The intervention was completed in 6 weeks or potentially earlier if the participant reports completion of their FIT.

Statistical analysis

All statistical analyses were performed using SAS 9.4. First, summary statistics were generated for all variables. Then bivariate analyses were conducted for key variables to compare differences between the intervention and control arms. Proportions calculated from categorical variables were compared using a chi-square test; means obtained continuous variables were compared using two-sample t-test. The multivariate analyses were conducted using the GEE procedure in SAS that implements the generalized estimating equations regression. Analyses were performed using an intent-to-treat approach that includes all participants randomized. Significance tests were two-sided and employed an overall significance level of $\alpha=0.05$. For each arm, the proportion of participants who receive CRC screening by 12 months was computed. The chi-square test was used to compare the two treatment arms for screening receipt. If the proportion of participants receiving CRC screening in the intervention arm is at least 15% higher than that in the control arm, the intervention will be determined to be effective. In addition, since our sample size gets small when participants are stratified by community health center or sex, we will use Fisher's exact test to assess the effect of the intervention. To assess the influence of key covariates (age, income, marital status, education, insurance status) on the primary outcome, logistic regression analysis was employed. In addition, to investigate treatment effects over time (baseline, 3 months, and 12 months), we will estimate hazard ratios by fitting Cox proportional models using time-varying covariates. In these models, the receipt of CRC screening will be regressed at each actual time point on time elapsed since baseline to test for an interaction between time and treatment group. The basic model will be repeated, adjusting for age, income, marital status, education, and any other significant covariates at baseline. To test the proportional hazard assumption, the Kaplan-Meier curve and the Schoenfeld residuals will be used for fixed and time-varying covariates, respectively.

Mediation and moderation analyses will be conducted to determine why and when variables are related, respectively. We will focus on specific mediators to include CRC perceived susceptibility, CRC self-efficacy, and CRC knowledge in the conceptual model.

The complexities of the relationships between the exogenous variables (X) and the endogenous variables (Y) as a function of the mediators will be examined using three separate regression models. We will ensure that the assumptions of continuous measurements (i.e., that all variables are measured on a continuous scale), normality (i.e., normal distribution of all variables), independence (i.e., that there is no correlation of errors from one observation to another observation), and linearity (i.e., evidence linear relationships among the variables) are met. We will assess direct causality and indirect causality using standardized regression coefficients (i.e., betas) to determine the direction and magnitude of the effect of one variable upon the other variable.

We will confirm that the mediators (i.e., CRC perceived susceptibility, CRC self-efficacy, and CRC knowledge) are caused by the exogenous variables X and are also the causes of the endogenous variables Y. We will also determine if X loses its significance when M is included in the model. Specifically, we will perform regression analyses and confirm the significance of the relationship between the exogenous (i.e., independent variable - IV) and endogenous variables (i.e., dependent variable - DV), the exogenous and mediator variable, the mediator and the endogenous variables in the presence of the IV, and lastly, we will confirm the lack of significance (or the meaningful reduction in effect) of the relationship between X and Y in the presence of the mediators.

Additionally, we will assess the moderator variables (i.e., sex, health literacy, family history of cancer) to determine under what condition (i.e., when) a given predictor X/independent variable (IV) is related to an outcome Y/dependent variable (DV). We will assess whether the moderation effect is enhancing (i.e., that is, increasing the moderator would increase the effect of the predictor on the outcome), buffering (i.e., that is, increasing the moderator would decrease the effect of the predictor on the outcome), or antagonistic (i.e., where increasing the moderator would reverse the effect of the predictor on the outcome). We will apply hierarchical multiple regression to examine the effects of the moderating variable. We will assess the interaction effect between X and M and whether or not such an effect significantly predicts the occurrence of Y. All variables will be standardized to facilitate data interpretation and avoid multicollinearity. We will fit a regression model predicting the outcome from both the predictor and moderator variables. We will check that both the effect of the predictor and the effect of the moderator, as well as the model (R²) are statistically significant. Then, we will fit another regression model that includes the interaction effect of the first model and check for a statistically significant R² change and a statistically significant effect of the interaction term to determine if moderation is occurring (i.e., both are statistically significant).

Mediation analysis allows assessment of each covariate's impact on the primary outcome independent of whether the intervention's effect is significant; thus, adding to scientific understanding of the relevance of each. To examine the mediating effects on the primary outcome of each of the short items scored on a Likert-type scale, we will follow the strategy of Baron and Kenny. We will conclude that the candidate covariate is indeed a mediator of the effects of the intervention if: (1) the treatment group indicator is significant; and (2) the candidate covariate is significant, and the coefficient estimate of the treatment group indicator is smaller in absolute value than its counterpart in analysis.

To assess the impact of candidate moderators, we will use Cox proportional hazard model and other appropriate survival analysis models to investigate the primary outcome on treatment group, each candidate moderator, and the interaction of treatment and each candidate moderator at each measurement time point.

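### The design is pretest/posttest, but the plan never says that the baseline score enters the comparison of knowledge or self-efficacy; a baseline-adjusted model would be more precise at no data cost

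*Combined protocol and SAP*

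**What the plan says.** The opening section, Study Protocol, sets out the design: "The TUNE-UP study is designed as a two-group pretest/posttest pragmatic randomized controlled trial". It reports that "115 participants were randomized at the time of enrollment following completion of the baseline survey", so a pre-randomization measurement exists for everyone. It then lists the secondary endpoints in one sentence: "Secondary outcomes included CRC knowledge and CRC screening self-efficacy". No instrument, score or follow-up time is attached to them. The 12-month and 3-month times in that section belong to the screening outcome.

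The Statistical analysis section has no sentence on the analysis of knowledge or self-efficacy as outcomes. Two sentences could apply to them:

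- As a general bivariate step for key variables, "means obtained continuous variables were compared using two-sample t-test". It does not say whether follow-up scores or change scores are meant.
- Multivariate analyses are said to use GEE. No outcome, covariate, time point or baseline term is given.

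The covariates listed for the logistic and Cox models are demographic, socioeconomic and insurance variables, and those models are for receipt of screening. Baseline knowledge and baseline self-efficacy are not among them. Otherwise the two scores appear only as candidate mediators. Randomization was stratified by the two community health centers (CHCs), under Randomization and blinding.

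**The concern.** A pretest/posttest design measures a score before randomization so that the follow-up comparison can use it. For a continuous score the usual way is to put the baseline value in the model as a covariate. Randomization keeps the estimate unbiased, and the adjustment removes the part of the follow-up variance that baseline explains. If the generic t-test is what is applied to knowledge and self-efficacy, that gain is lost, in a trial with only about 57 participants per arm.

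The comparison is also left open. A t-test on raw follow-up scores, a t-test on change scores and a GEE model with or without baseline are all compatible with the text, and they can give different estimates and different standard errors.

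**Working it through.** The documents give no power, SD, effect size or correlation for the secondary outcomes, so there is no planned figure to reproduce. The check compares the precision of the three candidate analyses.

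**Inputs from the documents**
- 115 randomized, with a "parallel group, two arm superiority trial design with 1:1 allocation ratio", so n = 115/2 = 57.5 per arm.
- "Significance tests were two-sided and employed an overall significance level of" 0.05.

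**Assumptions not in the documents**
- Baseline-to-follow-up correlation r of 0.3, 0.5 or 0.7.
- Equal SD at both times, the same r in both arms, complete follow-up and a normal approximation.
- A true effect of 0.5 SD, for the power illustration only.

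**Formulas, in units of the score's SD**
- Standard error of the difference in follow-up means: √(2/n) = √(2/57.5) = 0.1865.
- Adjusted for baseline: multiply by √(1 − r²).
- Change scores: multiply by √(2(1 − r)).
- Minimum detectable difference (MDD) at 80% power: (1.960 + 0.842) × standard error. For the follow-up t-test this is 2.802 × 0.1865 = 0.52 SD.

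**Results**

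| r | √(1 − r²) | Fall in SE against follow-up t-test | Equivalent unadjusted total, 115/(1 − r²) | MDD, follow-up t-test | MDD, change-score t-test | MDD, baseline-adjusted |
|---|---|---|---|---|---|---|
| 0.3 | 0.954 | 5% | 126 | 0.52 | 0.62 | 0.50 |
| 0.5 | 0.866 | 13% | 153 | 0.52 | 0.52 | 0.45 |
| 0.7 | 0.714 | 29% | 225 | 0.52 | 0.41 | 0.37 |

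Power for an assumed 0.5 SD effect is 76.5% with the follow-up t-test. With change scores it is 62%, 76.5% and 93% at the three correlations. With baseline adjustment it is 80%, 87% and 96%.

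**Why the adjusted model is not beaten.** Its standard error relative to change scores is √(1 − r²)/√(2(1 − r)) = √((1 + r)/2), which is below 1 for every r below 1: 0.81, 0.87 and 0.92 here. Relative to follow-up scores it is √(1 − r²), which is below 1 unless r is zero. The change score is worse than ignoring the pretest when r is below 0.5. The adjusted model spends two further degrees of freedom (baseline and CHC), leaving 115 − 4 = 111 against 113 for the t-test, a negligible cost.

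**The case against.** The strongest reply is that the plan does not exclude the pretest. A reader might infer that it collects the baseline scores and then discards them. The text does not support that. The t-test sentence is a general step that follows the summary statistics, and it does not name the secondary outcomes. It could be run on change scores, which would use the pretest. GEE suits repeated scores and could include baseline. This stands: the plan is silent on the pretest. But neither reading is written down, and even the change-score reading is less precise than the adjusted model, so the recommendation does not depend on which was meant.

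A reader might also infer that chance imbalance at baseline biases the t-test. It does not. With arms of 58 and 57, the baseline means can differ by up to 1.96 × √(1/58 + 1/57) = 0.37 SD at the 95% limit, and at r = 0.5 half of that, 0.18 SD, would carry over to follow-up. But that variation is already in the t-test's standard error. It is the same loss of precision as in the table, not a second harm.

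Finally, a reader might infer that the result could be picked from 3 or 12 months, and that 3 months should be named. The stated times attach to screening. No section says that knowledge or self-efficacy was measured at either time, or how often. The missing time is a missing detail, and the documents give no basis for choosing one.

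**Conclusion.** The point holds as a specification gap with a clear gain in precision available. The plan describes a pretest/posttest trial, states only a generic two-sample t-test for continuous means, and nowhere says that baseline enters the comparison of knowledge or self-efficacy. Against a t-test on follow-up scores, baseline adjustment lowers the standard error by about 5%, 13% or 29% for an assumed correlation of 0.3, 0.5 or 0.7. It is also more precise than a change-score t-test at each of these correlations. The size rests on correlations that the documents do not give, and at the low end the gain is small.

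The unadjusted test would be valid, so this is not a claim of bias. It concerns secondary outcomes only: the comparison of screening receipt by 12 months does not change. It assumes that the baseline survey contains the same knowledge and self-efficacy items, which the pretest/posttest label implies but no sentence confirms, and that the scores are treated as continuous.

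**What to change.** In the Statistical analysis section, add one paragraph for the two secondary outcomes:

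- For both knowledge and self-efficacy, replace the two-sample t-test with a linear model of the follow-up score on arm, baseline score and CHC (the randomization stratum). Report the adjusted difference between arms with its 95% interval.
- If GEE is used because the scores were repeated, say so and include the baseline score and CHC in that model.
- Name the follow-up time or times at which each score was actually measured.

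The cost is text only if the baseline survey holds the same items: no new data and no new visit. The document is dated 1/26/2022 and already describes randomization and some analyses in the past tense. If this analysis is set after the comparative data on these outcomes were seen, it should be labeled post hoc.

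### The stated overall 0.05 significance level holds for the 12-month chi-square test but not for the wider set of planned tests, which has no formal multiplicity control or testing order

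*Combined protocol and SAP*

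**What the plan says.** The error-rate statement is one sentence in Statistical analysis: "Significance tests were two-sided and employed an overall significance level of" 0.05. The same document plans the following.

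- **Primary outcome.** The Study Protocol section names screening by 12 months. Statistical analysis adds: "The chi-square test was used to compare the two treatment arms for screening receipt". Next to this stands a rule that calls the intervention effective if its screening proportion exceeds the control arm's by 15% or more. The rule mentions no p-value and does not say whether 15% is relative or in percentage points.
- **3 months.** Screening at 3 months is called an intermediary outcome.
- **Subgroups.** The intervention effect is assessed by Fisher's exact test within each of the two health centers and each sex, which makes four tests.
- **Other models of screening.** Cox models, basic and adjusted, examine treatment effects over time. Logistic regression examines covariates. GEE is named without an outcome or role: "The multivariate analyses were conducted using the GEE procedure in SAS".
- **Secondary outcomes.** "Secondary outcomes included CRC knowledge and CRC screening self-efficacy".
- **Mediators and moderators.** There are three of each, and conclusions depend on terms being significant. The moderator models include "the interaction of treatment and each candidate moderator at each measurement time point".

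The document gives no split of alpha, testing order or multiplicity adjustment, and it does not label any analysis exploratory.

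**The concern.** An overall level of 0.05 says that the chance of any false positive in the set is at most 5%. That needs either a single confirmatory test or a procedure that controls error across several. The plan states neither, so the sentence reads as if it covered every test listed.

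What is at stake is how isolated findings are reported. With 115 participants, and strata that the plan itself regards as small, one significant site, sex, 3-month or moderator result is a realistic chance event. Under the present text it could be presented as significant at an overall 5% level. The plan also does not say what to conclude if the chi-square test and the 15% rule disagree.

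**Working it through.** **Inputs from the document.** Two-sided 0.05; "115 participants were randomized at the time of enrollment following completion of the baseline survey"; 1:1 allocation; two sites; two secondary outcomes; three moderators.

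**Assumptions not in the document.** Arms of 58 and 57; the same 12-month screening rate in both arms, at 30%, 50% or 70%; 60% of screening done by 3 months; sites 50/50; sex 60/40; health literacy 50/50; family history 40/60; secondary outcomes correlated 0.4 with each other and independent of screening.

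**Step 1: the stated figure.** For one test, 1 − (1 − 0.05) = 0.05. The exact binomial size of the 12-month chi-square test with 58 and 57 participants is 0.050 at 30% and 70% screening and 0.051 at 50%. The stated level is therefore reproduced for this test alone.

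**Step 2: the wider set.** If k tests were independent, the chance of at least one p<0.05 would be 1 − 0.95^k. The planned tests are correlated, so this overstates the rate. The last column comes from 4,000 simulated null trials per screening rate, with a two-interval log-rank test standing in for Cox.

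| Tests included (cumulative) | k | 1 − 0.95^k | Simulated |
|---|---|---|---|
| 12-month chi-square | 1 | 5.0% | 4.7–5.3% |
| + 3-month chi-square | 2 | 9.8% | 8.3–9.7% |
| + time-to-event test | 3 | 14.3% | 8.4–10.1% |
| + four Fisher tests | 7 | 30.2% | 15.3–17.0% |
| + two secondary tests | 9 | 37.0% | 23.2–24.9% |
| + three moderator interactions | 12 | 46.0% | 32.1–33.7% |

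Monte Carlo standard error is √(0.05 × 0.95/4000) = 0.3 points at 5% and √(0.33 × 0.67/4000) = 0.7 points at 33%. Each Fisher test is conservative (2.6–3.9% on its own), and the subgroups overlap with the whole sample. Four of them therefore add about 7 points, not 20.

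**Step 3: sensitivity.** A second null simulation used 6,000 trials per setting, with screening of 15%/30% or 25%/45% at 3/12 months. It gave 5–6%, 9%, 9–10% and 16–17% for the first four rows, in close agreement. It then gave 31% and 40% for the last two, because it tested each secondary outcome at two times and took the two outcomes as independent of each other. The document does not say when these outcomes are compared, so the full-set figure is best given as about 32–40%.

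**Step 4: the 15% rule.** Under no effect, the exact chance that the intervention arm meets the rule is:

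| Screening rate | 15 percentage points | 15% relative | Points rule and chi-square p<0.05 |
|---|---|---|---|
| 30% | 4.7% | 31.3% | 2.5% |
| 50% | 4.7% | 22.9% | 2.5% |
| 70% | 3.6% | 12.9% | 2.5% |

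The rule looks in one direction only, so the fair comparison is the 2.5% that a two-sided 0.05 test allows in the intervention's favor. The difference needed for significance is about 1.96 × √[p(1 − p)(1/58 + 1/57)]. This is 1.96 × 0.0933 = 0.183 at 50% and 1.96 × 0.0855 = 0.168 at 30% or 70%. An observed difference between 15 and about 17–18 points would thus meet the rule without being significant.

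**The case against.** The strongest reply is that the trial does have a primary test and that its error rate is intact. The Study Protocol section ranks the outcomes as primary, intermediary and secondary. Statistical analysis names chi-square for comparing the arms and gives a rule for declaring effectiveness. Nothing says that a win on a subgroup, secondary outcome or moderator counts as trial success, and the mediation and moderation work is framed as explanatory.

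Much of this stands, and it rules out several stronger readings that a reader might infer:

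- *That there is no hierarchy, or that nothing says which analysis decides.* There is an informal ranking, and the effectiveness rule involves neither logistic regression nor Cox. What is missing is a formal order or adjustment, and a link between that rule and the test.
- *That the primary test is inflated.* It is not: it keeps its 5%.
- *That analyzing screening in several ways drives the problem.* Logistic regression is aimed at covariates, and the test described for the Cox models is a time-by-treatment interaction. In the simulation a time-to-event test adds only 0.1–0.4 points.
- *That 40% is an established figure.* It needs secondary outcomes tested at two times and independent of each other, which the document does not state. A separate 3-month arm test is also implied, not specified. The simulated moderator tests leave out the preliminary significance checks required in the hierarchical regression, although the Cox moderator analysis has no such checks. They also leave out repetition across time points.

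The reply does not rescue the word *overall*. The subgroup tests are described as assessing the intervention effect, mediator and moderator conclusions rest on significance, and the plan says that the mediation analysis is informative whether or not the intervention effect is significant. These tests are therefore not conditional on the primary result.

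**Conclusion.** The point holds as a mismatch between the stated level and the planned set of tests. The 5% level is right for the 12-month chi-square test and unsupported as an overall level. Adding the 3-month and subgroup tests takes the chance of a false positive to about three times the stated 5% (15–17%), and the full set to at least six times (32/5 = 6.4).

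The 12-month test's own size was calculated exactly and changes little across the rates tried. The wider figures depend on assumed screening rates, splits and correlations, and the last two steps also depend on how often secondary outcomes and moderators are tested. Mediation tests, GEE and the adjusted models were not simulated.

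The unlinked 15% rule matters as well: read as a relative difference, it would be met by chance in 13–31% of trials with no effect. The matter should be corrected, but it does not invalidate the primary comparison.

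**What to change.** In Statistical analysis:

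1. Replace the overall-level sentence with a statement that the chi-square comparison of arms on screening by 12 months is the sole confirmatory test, at two-sided 0.05.
2. State whether 15% is relative or in percentage points and how it relates to that test, so that there is one criterion for effectiveness. Without this, step 1 leaves two.
3. Report the 3-month, Cox, GEE and logistic results as supportive, with estimates and 95% confidence intervals.
4. Report knowledge and self-efficacy as secondary. Either test them only after a significant primary result (for example with Holm) or give confidence intervals with no confirmatory claim. Either is acceptable; Holm is not essential.
5. Label subgroup, mediation and moderation results exploratory.

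This needs no new data and costs the primary test no power. A Bonferroni split over the 12 tests simulated would instead run each at 0.05/12 = 0.0042. The price is that a lone significant 3-month, subgroup, secondary or moderator result can no longer be claimed as confirmed. The document describes the primary comparison in the past tense. If that analysis has already been run, the ordering must be disclosed as post hoc.

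### Randomization is stratified by health center, but the primary chi-square and the named model covariates leave center out; the test stays valid but turns conservative if the centers' screening rates differ materially

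*Combined protocol and SAP*

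**What the plan says.** **Design.** Under Randomization and blinding: "The trial randomized participants at the individual level, stratified by the two CHC sites", at 1:1. Also: "The randomization algorithm used randomly permuted blocks with random block sizes". CHC is the only stratification factor.

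**Analysis.** All of the following are under Statistical analysis.

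- Primary test: "The chi-square test was used to compare the two treatment arms for screening receipt". No stratification is mentioned.
- Effectiveness rule, based on the point estimate: "If the proportion of participants receiving CRC screening in the intervention arm is at least 15% higher than that in the control arm".
- Logistic model: "key covariates (age, income, marital status, education, insurance status) on the primary outcome, logistic regression analysis was employed". CHC is not listed.
- Adjusted Cox model: "adjusting for age, income, marital status, education, and any other significant covariates at baseline". CHC is not named.
- GEE: "The multivariate analyses were conducted using the GEE procedure in SAS". Neither covariates nor a cluster variable are given, so the role of CHC there is unknown.
- The one use of CHC: "since our sample size gets small when participants are stratified by community health center or sex, we will use Fisher's exact test". Nothing says how the two center results would be combined.

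The moderators named later in the section are sex, health literacy and family history of cancer. CHC is not among them.

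**The concern.** Blocking within center removes between-center variation from the true sampling variance of the difference between arms. The pooled chi-square still counts that variation. If screening rates differ between centers, its standard error is too large, its real size falls below 5%, and power is lost. A center difference is plausible: the outcome is receipt of a stool-based test, and the center supplies the kit by mail, in person or at a visit.

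There is also a prespecification gap. CHC can reach the Cox model only through the open-ended clause on significant baseline covariates. If significant means imbalance between arms, stratified blocks keep CHC from ever qualifying. If it means association with outcome, the model is chosen from the data.

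At stake are a few points of power in a trial that has little to spare, and the lack of any overall treatment estimate that follows the design.

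**Working it through.** The plan states no power, assumed rates or sample-size derivation, so there is no figure of its own to reproduce.

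**Inputs from the documents.** 115 randomized; 1:1 allocation in permuted blocks within two centers; binary outcome at 12 months; two-sided 5% level; a 15% margin, read here as 15 percentage points.

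**Assumptions.** Center sizes 58/57 or 80/35; block sizes 2, 4 and 6; mean control rate 30% or 40%; the same risk difference in both centers; a range of center gaps.

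**Step 1: size by formula.** With center weights w and center rates p_c, the ratio of the true variance to the variance used by the chi-square is

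R = Σ w·p_c(1 − p_c) / [p(1 − p)], and actual size = 2·[1 − Φ(1.96/√R)].

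Example with equal centers at 20% and 60%: the numerator is 0.5(0.16) + 0.5(0.24) = 0.20 and the denominator is 0.4 × 0.6 = 0.24. So R = 0.833, 1.96/√0.833 = 2.147, and the size is 3.18%.

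**Step 2: exact enumeration.** N = 115, equal centers, mean control rate 40%; the power columns use a 20-point effect.

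| Center rates | R | Size by formula | Exact size, chi-square | Exact size, CMH | Power, chi-square | Power, CMH |
|---|---|---|---|---|---|---|
| 40/40 | 1.000 | 5.00% | 5.46% | 5.22% | 57.7% | 56.7% |
| 35/45 | 0.990 | 4.88% | 5.34% | 5.26% | 57.3% | 58.6% |
| 30/50 | 0.958 | 4.53% | 4.96% | 5.15% | 57.0% | 60.5% |
| 25/55 | 0.906 | 3.95% | 4.36% | 4.95% | 56.7% | 62.1% |
| 20/60 | 0.833 | 3.18% | 3.54% | 4.98% | 56.3% | 65.8% |

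The small excess over 5% at equal rates comes from the discreteness of the Pearson test, not from stratification.

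**Step 3: simulation at the plan's own margin.** 20,000 trials per scenario with a 15-point effect. Ranges span the assumed splits and control rates. The base case is 58/57 with a 30% mean control rate.

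| Center gap (points) | CMH minus chi-square power (points) | Base-case power, chi-square v CMH | Chi-square size | Base-case 95% CI half-width, crude v stratified (points) |
|---|---|---|---|---|
| 0 | -1.0 to -0.5 | 39.6% v 39.1% | – | – |
| 10 | -0.3 to +0.2 | – | – | – |
| 20 | +0.6 to +2.1 | – | 4.2–5.0% | 17.3 v 16.8 |
| 30 | +2.4 to +3.8 | 38.8% v 41.5% | 3.7–4.5% | 17.3 v 16.3 |
| 40 | +5.1 to +6.9 | 38.7% v 45.0% | 3.1–3.9% | 17.3 v 15.6 |

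CMH size was 4.6–5.3%. Repeat runs with the same settings put the gain at about 2 to 4 points for a 30-point gap and 4 to 7.5 points for a 40-point gap.

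**Step 4: the effectiveness rule.** Crude and stratified differences fell on opposite sides of 15 points in about 0.4–4.5% of trials, so the rule is nearly unaffected.

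**Step 5: logistic model with and without CHC.** Base case, 30-point gap, 4,000 trials, arm as the only other term: size 3.9% v 5.5% and power 38.6% v 42.7%. Part of that gain comes from a slightly liberal test.

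**Step 6: do the within-center Fisher tests fill the gap?** For 30% v 45% with 29 per arm, exact power is 14%. For centers of 35 to 80 participants and control rates of 20–40%, it is 11–25%.

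**Step 7: can CHC qualify as imbalanced?** With blocks of at most 6, the worst 58/57 allocation is 30 v 28 and 27 v 30. The chi-square is 115·(30·30 − 28·27)² / (58·57·57·58) = 0.218, so p = 0.64. For 80/35 the worst is 41 v 39 and 16 v 19: 115·(41·19 − 39·16)² / (80·35·57·58) = 0.298, so p = 0.59. CHC could never test as significant between arms.

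The Cox and GEE models were not simulated.

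**The case against.** The strongest reply is that this is a small efficiency preference. Below a gap of about 20 points, CMH gains almost nothing or loses slightly. At 20 points with a true 15-point effect, the two tests gave different significance calls in only about 1–3% of trials. A material loss needs something like 45% v 15% between control groups. The two centers serve one area under common eligibility criteria, with one brochure and one community health advisor, and nothing in the documents points to a gap that large. This stands, and it is why the point is conditional and not a validity objection. It does not favor leaving the stratum out, because the most that stratifying costs is about 1 point of power.

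Timing is a fair objection too. Parts of the section are in the past tense, so outcomes may already have been seen. Replacing the primary test would then be post hoc, and the fix has to allow for that.

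The case for changing the models is weaker than the case for the CMH test. Income and insurance status, already in the logistic model, could absorb part of a center difference, so the gain in Step 5 need not carry over. The GEE covariates are unstated, so an omission there cannot be shown. A longer Cox list has a cost that was not assessed: at 30% v 45% there would be about 57.5 × (0.30 + 0.45) = 43 events.

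Finally, the open-ended Cox clause is a prespecification matter in a secondary model. It adds nothing to the weight of the point about the primary test.

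**Conclusion.** The concern holds as stated. The plan randomizes within CHC and gives no prespecified, CHC-adjusted comparison of the arms. The pooled chi-square protects type I error. It becomes conservative only if center rates differ materially: at a 30-point gap its size is about 3.7–4.5% and it gives up roughly 2 to 4 points of power; at 40 points, about 3.1–3.9% and 5 to 7 points. At 10 points or less nothing is gained by stratifying. These figures rest on assumed center sizes, rates and block sizes and on a constant risk difference. Confidence in the size of the loss is therefore medium, while the omission itself is plain from the text. The change is worth making but does not rescue the trial's power, which stays at about 35–45% for a 15-point effect.

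**What to change.** 1. Make the primary test a CMH test stratified by CHC. Beside the 15% rule, report the CHC-stratified (Mantel-Haenszel-weighted) risk difference with its 95% confidence interval.
2. Add CHC to the logistic and GEE models. In the Cox model, add it as a covariate or stratify by it; stratifying adds no coefficient, which helps with few events.
3. Replace the open-ended Cox clause with a fixed list: CHC, insurance status, education, income, age and marital status. Check its length against the expected number of events.
4. Keep the within-center Fisher tests as descriptive subgroup results.
5. If outcome data have already been seen, leave the chi-square as primary and report the stratified analysis as a labelled sensitivity analysis.

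**Cost.** A change of SAP wording and a few lines of SAS, with no new data. Up to about 1 point of power is lost if the centers turn out to be identical.
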